8.4 Missing Data

(ICH E3; 9.7.1, 11.4.2.2. ICH E9;5.3. EMA Guideline on Missing Data in Confirmatory Clinical Trials)

During ongoing quality control of data entered in the study database, data from a study visit is reviewed by the study registry coordinator within 2 weeks of being entered and queries are sent to the site regarding any missing or apparently spurious data. Once these queries are answered satisfactorily, the data for that visit is locked. Only data contained in locked visits will be used for trial analyses.

In preparation for the interim and final analyses, the study statistician will perform further examination of the data for outlier values. Values outside a plausible range (e.g. an erythrocyte sedimentation rate >200 mm/h) will be converted to missing values.

After receiving the locked study dataset for the final analysis and dealing with values outside a plausible range, missing values will be imputed if needed using multiple imputations by chained equations.

Missing MISS questionnaire scores will not be imputed. Subjects with missing MISS questionnaire scores while still receiving methotrexate will be considered as censored as of the last available visit with a valid MISS score.

8.5 Interim Analyses and Data Monitoring

(ICH E3; 9.7.1, 11.4.2.3. ICH E9; 4.1, FDA Feb 2010 “Guidance for Industry Adaptive Design Clinical Trials for Drugs and Biologics”)

The OPT-JIA protocol (V3, September 2, 2020) called for a preliminary analysis to be used by an independent data and safety committee (DSC) to review for any needed adjustments to the target sample size, or early termination of the trial.

The interim analysis was to be conducted once 90 patients had been recruited to the trial. All follow-up information available at that point was to be used to calculate a two-sided 95% confidence interval (CI) for the relative risk of continuing on methotrexate with no intolerance, where the confidence level is adjusted for information accrual as per Schoenfeld [15].

8.5.1 Purpose of Interim Analyses

The purpose of the interim analysis is to obtain a preliminary assessment of efficacy to assess trial progress to date, deciding whether to continue the trial and/or re-estimate the sample size. Decisions arising from the interim analysis include continuing to the original planned sample size, changing the sample size respecting the evidence gathered to date, or terminating the trial. Termination could be either because of overwhelming evidence of superiority of the ondansetron intervention or because of statistical futility measured by overwhelming evidence that the intervention did not improve retention on methotrexate without intolerance.

8.5.2 Planned Schedule of Interim Analyses

The single interim analysis was originally planned after recruitment of 90 children. As explained in the scope of adaptation below, due to slower than expected recruitment this was changed in the spring of 2023 by the OPT-JIA Steering Committee in consultation with the Data and Safety

Committee to be conducted with patients recruited as of September 30th, 2023, irrespective of the number of subjects.

8.5.3 Scope of Adaptations

The trial steering committee, with approval from the DSC, elected to conduct the interim analysis at an earlier stage of the trial than initially planned. Because of challenges relating to the COVID19 pandemic and other reasons, recruitment into the study had been much slower than anticipated, and there were concerns that the initial planned sample size might be unattainable within a reasonable time frame. The interim analysis was rescheduled to take place using all available enrolments into the study as of September 30, 2023.

Because the analysis would be based on a much smaller fraction of the intended sample size, the OPT-JIA PI and the study statistician proposed, and the DSC agreed, to base the analysis on the confidence interval for relative risk computed using the ratio of two estimates of the probability of successful trial completion from independently estimated Kaplan Meier curves. These estimates would better account for the partial information available from patients who did not have sufficient time in the study to complete the 52-week observation period.

To make use of all available information from patients who had not completed the trial yet, the definition of the primary end point was modified as follows. Visit times were shown in weeks since enrolment in OPT-JIA. We used 52 weeks to represent the 1-year visit as required for determining success. Failure was determined to have occurred if any of the criteria for failure -- stopping methotrexate or experiencing intolerance -- were observed during any visit up to and including 52 weeks. Success was determined to have occurred if no failure criteria were met at or before 52 weeks, and the patient had at least one visit at or after 52 weeks. All other patients were considered censored as of the time of their last visit; i.e., they were known not to have failed yet, but they had not yet provided a visit at or beyond 52 weeks to declare success.

The second adaptation was the use of the O'Brien-Fleming adjustment to type 1 error rate for the calculation of the confidence interval in the interim analysis [17]. This adjustment resulted in calculation of a 99.55% confidence interval for the interim analysis instead of the 95% mentioned in the protocol. The rationale being that both the interim and the final analysis together would then have a 5% chance of a positive result if the intervention is no more effective than control.

8.5.4 Stopping Rules

As per the study protocol, the Data and Safety Committee assess results of the preliminary analysis according to the following guidance:

- If the CI is entirely below a relative risk of 1.2, the study will be stopped for futility.
- If the CI is entirely above a relative risk of 1.2, the study will be stopped and superiority will be claimed.
- If the CI includes a relative risk of 1.2, the trial will continue until the re-calculated full target sample is attained.

The RR of 1.2 was selected on clinical grounds. In a prospective study of 142 children with JIA starting methotrexate followed for one year, Van Dijkhuizen et al reported that 59 patients developed intolerance and 11 discontinued methotrexate for other reasons, for a total of 72 (50.7%) remaining on methotrexate with no intolerance [18]. An increase in this proportion to <60% is deemed too small to justify the additional costs and risks of adding prophylactic ondansetron.

8.5.5 Analysis Methods to Minimize Bias

Although OPT-JIA is not a blinded RCT, the two components of the primary endpoint are robust and unlikely to be influenced directly by the OPT-JIA investigators or the statisticians. Whether a patient is receiving methotrexate or not is a verifiable occurrence not under their control, and intolerance is defined directly by the parents by answering a validated questionnaire. Further, there is no pharmaceutical sponsor for OPT-JIA and the medications being tested have been marketed as generic medications in Canada for >20 years, making bias introduced by a pharmaceutical sponsor not possible.

8.5.6 Adjustment of Confidence Intervals and p-values

We use the O'Brien-Fleming adjustment to type 1 error rate for the interim analysis. This adjustment is based on the “alpha-spending” principle that guarantees that no conclusions from the trial have more than a 5% chance of a positive result if the intervention is no more effective than control. The adjustment uses a substantially reduced alpha level for the interim analysis, making it more difficult to terminate the trial prematurely due to chance outcomes. The final analysis of the primary outcome uses the remaining alpha not used (0.05 minus the amount used in the interim, 0.0045), and combines the data from both stages of the trial into one final test statistic.

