8.5.7 Interim Analysis for Sample Size Adjustment

Upon completion of the interim analysis, a new sample size estimate is calculated using simulation techniques. Simulation answers the following question: given our current data, and assuming that our initial expectations for success probability in the two arms remain true (75% in intervention, 50% in control), how many more patients would need to be enrolled in order to maintain a 90% chance that the final analysis produces a 95% confidence interval for the relative risk that lies entirely above 1.2?

We use simulation techniques because the binary success/failure outcome is easy to simulate accurately from any expected probability specifications and for any size of patient sample. The simulation involves creating hypothetical future results using the expected success probabilities for a new set of n patients in each treatment group, adding the current results to these simulated future results, conducting the final analysis on the complete set of results, and observing whether the confidence interval lies entirely above 1.2. We perform this simulation and analysis process 10,000 times, and the proportion of these replicates in which the interval lies above 1.2 is an accurate estimate of the power for the study using n new patients per group. By repeating the process for a variety of values of n , we can identify the smallest sample size that achieves 90% power.

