Our primary outcome statistic is the ratio of two proportions (relative risk, RR): the proportion of randomized children remaining on methotrexate with no intolerance one year after enrolment in the intervention group divided by the same in the control group. Subjects stopping ondansetron or methotrexate for toxicity or lack of efficacy will be counted as trial failures in calculations for the primary endpoint, irrespective of their MISS scores. A 95% CI for the RR will be calculated and the null hypothesis will be rejected if the confidence interval is entirely above 1. Considering that an interim analysis will be conducted, the alpha used in the final analysis will be 0.05 minus the alpha used in the interim analysis. As stated above, due to patient withdrawals and the fact that OPT-JIA did not have fixed-date visits, a number of patients was expected not to have a documented primary endpoint within the 52-week window, and a decision was made to use instead the Kaplan Meier estimates of the probability of success for calculations of the relative risk.

Cumulative incidence of methotrexate intolerance within one year: The Kaplan Meier survival analysis estimate of the cumulative incidence of a MISS score of 6 or more points within 52 weeks of study enrollment, as defined above. Kaplan-Meier curves will be constructed separately for intervention and control groups and the curves will be compared using the log-rank test.

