With the agreement of the Steering Committee and the Data and Safety Committee, the interim analysis took place at an earlier stage than initially specified because of the slow enrolment into the study. The interim analysis was planned by [name] with the assistance of [name] and discussed with the PI, [name], in March 2023. It was discussed and approved at the steering committee call of April 21, and at the Data and Safety Committee call on May 8, 2023, and further confirmed with the DSC chair via email on October 5, 2023. The approved plan was to extract information from the REDCap database on September 30, and this was postponed to October 6, to allow time for responses to remaining queries to be verified by site principal investigators. The sample sizes for the interim analysis were smaller than had been expected, and hence there were only 27 patients on whom success or failure had been definitively determined at the time the interim analysis was conducted with data extracted on October 6th, 2023. There were an additional 17 participants who were still on the trial, with at least one follow-up visit but not yet to their 52-week visit. We therefore used the Kaplan-Meier (KM) statistical analysis technique separately in each group to estimate the probability of success in each group in a way that would make some use of the partial information provided by the patients with incomplete follow-up periods.

We used the KM method to estimate the probability of success at 52 weeks and formed the relative risk (RR) by dividing the estimated probability for the intervention group by the estimated probability for the control group. The statistical properties of the RR are better expressed on the log scale, so we computed the log of this ratio, which is equivalent to the difference between the two logged survival probabilities. We computed the standard error for this difference using the separate standard errors for each logged survival probability and computed the confidence interval on this log scale using the standard normal (Wald) method. The same KM methods will be applied for the final efficacy analysis.

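### The final test is set at alpha 0.0455, but section 10.1 rejects on, and section 8.5.7 sizes on, a 95% confidence interval; the matching interval is 95.45%

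*SAP*

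**What the plan says.** The SAP gives the level of the final primary test in several places.

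- **Section 8.5.6** subtracts the interim alpha: "The final analysis of the primary outcome uses the remaining alpha not used (0.05 minus the amount used in the interim, 0.0045". It says the adjustment "guarantees that no conclusions from the trial have more than a 5% chance of a positive result".
- **Section 10.1** gives the decision rule: "A 95% CI for the RR will be calculated and the null hypothesis will be rejected if the confidence interval is entirely above 1". The sentence that follows says "the alpha used in the final analysis will be 0.05 minus the alpha used in the interim analysis".
- **Section 8.5.7** asks how many more patients are needed for a 90% chance that "the final analysis produces a 95% confidence interval for the relative risk that lies entirely above 1.2".
- **Section 8.5.3** translates alpha into an interval level for the interim look: "This adjustment resulted in calculation of a 99.55% confidence interval for the interim analysis instead of the 95% mentioned in the protocol".
- **Section 15** describes a Wald interval on the log relative risk, built from Kaplan-Meier estimates, and adds: "The same KM methods will be applied for the final efficacy analysis".
- **Mock Table 4** labels the interval for the relative risk as 95%.

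**The concern.** In this SAP the confidence interval is the test: the null is rejected, or not, according to where the interval lies. The level of the interval is therefore the significance level. A 95% interval tests at 0.05, and a test at 0.05 − 0.0045 needs a wider interval. The SAP made this conversion for the interim analysis (0.0045 became 99.55%) but not for the final one.

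Two things follow. First, a result with p between 0.0455 and 0.05 has no settled interpretation. The trial is open-label and the analysts have already seen interim results, so that choice should not be left until the final data are known. Second, if the final test is run at 0.0455, a sample size chosen by simulating a 95% interval falls a little short of its own 90% power target.

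**Working it through.** **Inputs.** Overall alpha 0.05 and interim alpha 0.0045 (8.5.6, 15). Success 75% against 50%, 90% power, 79 evaluable per group (section 7). Bound of 1 for the final test (10.1) and of 1.2 for re-estimation (8.5.7).

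**Level of the interval.** A two-sided Wald interval that tests at level α has confidence 1 − α.

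- Interim: 1 − 0.0045 = 0.9955, so 99.55%. This reproduces the figure in 8.5.3.
- Final: 0.05 − 0.0045 = 0.0455, and 1 − 0.0455 = 0.9545, so 95.45%.
- Critical values: 1.960 for 0.05, 2.000 for 0.0455, 2.841 for 0.0045.

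**A result that splits the two readings.** Take 57/79 against 45/79, with complete follow-up.

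- RR = 57/45 = 1.267; log RR = 0.2364.
- SE = √(1/57 − 1/79 + 1/45 − 1/79) = 0.1202.
- z = 0.2364/0.1202 = 1.967; p = 0.0492.
- 95%: exp(0.2364 ± 1.960 × 0.1202) = 1.001 to 1.603, so reject.
- 95.45%: exp(0.2364 ± 2.000 × 0.1202) = 0.996 to 1.611, so do not reject.

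**Power and sample size.** The figures below are the exact binomial probability that the lower log-RR Wald limit exceeds the bound, at 75% against 50% with complete follow-up and no interim data added.

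| Criterion | 95% CI | 95.45% CI |
|---|---|---|
| Bound 1: power at 79 per group | 90.3% | 89.6% |
| Bound 1: smallest n per group for 90% | 79 | 81 |
| Bound 1.2: smallest n per group for 90% | 267 (90.1%) | 273 (90.1%) |
| Bound 1.2: power at 267 per group | 90.1% | 89.4% |

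At 95% and bound 1 this calculation returns the SAP's own 79 per group. The large-sample formula n = (z_α + 1.2816)² × [(0.25/0.75) + (0.5/0.5)] / (log 1.25)² for the 1.2 bound gives 282 and 289 per group instead of 267 and 273. The absolute numbers depend on the method, but the relative increase is similar: 273/267 = 1.022 and 289/282 = 1.025.

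**Type I error.** The interim claims success only if the 99.55% interval lies wholly above 1.2 (8.5.4). Assume 22 per arm at the interim, 50% success in both arms and non-binding futility. Exact two-stage enumeration then gives a 0.000009 chance of an interim claim. The overall two-sided error is:

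- 79 per group: 4.6% under either reading.
- 267 per group: 5.1% with a 95% final interval, 4.2% with 95.45%.

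If the interim had instead been tested against RR = 1 at 0.0045, a 95% final interval would give 5.35%, 5.29% or 5.16% at information fractions of 0.153, 0.278 and 0.511.

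**The case against.** The strongest defence is that 10.1 corrects itself. Its 95% rule is nominal, and the next sentence adjusts it. Section 8.5 uses a similar form for the original interim plan, naming a 95% interval and then saying its confidence level is adjusted. Section 8.5.6 writes the subtraction out, so a careful reader can infer 0.0455. The SAP's subtraction is also correct in itself, so the fault is a failure to carry it through.

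That shows which level was probably meant, but it does not repair the text. The decision rule still names 95%, and 8.5.7 has no neighbouring sentence to adjust its criterion. Section 8.5.3 shows that the SAP states the converted level when it means to.

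The objections on size largely stand:

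- The two readings disagree in under 1% of trials at 79 per group under the design assumptions (90.3% against 89.6%).
- The contrast of 5.1% with 4.2% at 267 per group is partly discreteness of the binomial at that one sample size, and should not be taken as the size of the problem.
- With 10,000 simulations the Monte Carlo standard error near 90% is √(0.9 × 0.1/10,000) = 0.3 points, so a shortfall of 0.6 points is about two standard errors.
- Section 8.5.7 adds current data to simulated data. Interim counts by arm are not given, so that calculation cannot be repeated here.
- A conventional 95% interval in a reporting table is not wrong in itself. Changing Table 4 serves consistency with the test.

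Subtraction is also slightly conservative, because it ignores the correlation between the two looks. So 0.0455 is the level the SAP's own rule implies, not the only valid one. The different bounds in 10.1 (1) and 8.5.7 (1.2) matter far more for sample size, but that is a separate point.

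**Conclusion.** The concern holds. By the SAP's own rule the final primary test is at 0.0455, so the 95% in the 10.1 rejection rule and in the 8.5.7 criterion is wrong as written; the matching interval is 95.45%. The practical effect is modest: about 0.7 points of power at 79 per group with bound 1, and 2 to 2.5% more children per group under the 1.2 criterion. Error control is not materially at risk, because the interim rule against 1.2 spends almost none of the alpha under either reading. These figures assume binomial outcomes with complete follow-up, no interim data carried forward and, for the two-stage error, 22 per arm at the interim. The planned Kaplan-Meier analysis will differ somewhat. The contradiction itself does not depend on these assumptions, and it should be corrected because it sits in the primary decision rule.

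**What to change.** Make 0.0455 the single level for the final primary test. Write 95.45% in the rejection rule of 10.1 and in the simulation criterion of 8.5.7, and rerun that simulation with the actual interim data. Show the 95.45% interval in the primary row of mock Table 4, so that the reported interval and the test agree.

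The cost is a few SAP edits and one rerun. The deciding interval becomes slightly wider. Keeping 90% power takes about 2 more children per group with bound 1 (81 against 79), or about 6 more with the 1.2 criterion (273 against 267) if all patients are new and follow-up is complete.

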8.5.7 Interim Analysis for Sample Size Adjustment

Upon completion of the interim analysis, a new sample size estimate is calculated using simulation techniques. Simulation answers the following question: given our current data, and assuming that our initial expectations for success probability in the two arms remain true (75% in intervention, 50% in control), how many more patients would need to be enrolled in order to maintain a 90% chance that the final analysis produces a 95% confidence interval for the relative risk that lies entirely above 1.2?

We use simulation techniques because the binary success/failure outcome is easy to simulate accurately from any expected probability specifications and for any size of patient sample. The simulation involves creating hypothetical future results using the expected success probabilities for a new set of n patients in each treatment group, adding the current results to these simulated future results, conducting the final analysis on the complete set of results, and observing whether the confidence interval lies entirely above 1.2. We perform this simulation and analysis process 10,000 times, and the proportion of these replicates in which the interval lies above 1.2 is an accurate estimate of the power for the study using n new patients per group. By repeating the process for a variety of values of n , we can identify the smallest sample size that achieves 90% power.

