6.4 Study Assessments

(ICH E3; 9.5.1. ICH E9; 2.2.2)

Visit	Baseline	Every Visit	Visit Month 12
History and examination	x	x	x
QOL questionnaire	x	x (\pm 14)	x (\pm 14)
MISS	x	x (\pm 14)	x (\pm 14)
Actionable AEs	x	x	x
SAEs	x	x	x
SUSARs	x	x	x
Concomitant medication	x	x	x
Methotrexate use and dose	x	x	x
Ondansetron use and dose	x	x	x

Analysis Time Windows

Visit (target day)	Lower bound (days)	Upper bound (days)
Baseline (0)	N/A	N/A
Every visit to clinic (time window not applicable)	N/A	N/A
Month 4-8 (180)	120	240
Month 12 (364)	308	420

7 Sample Size

(ICH E3; 9.7.2. ICH E9; 3.5)

Our primary outcome statistic is the ratio of two proportions (relative risk, RR): the proportion of randomized children remaining on methotrexate with no intolerance in the intervention group divided by the same in the control group. Our sample size calculation is based on expressing the RR in the log scale and using established formulas for standard errors [15, 16]. With $p<0.05$, power of 90% and expected methotrexate continuation with no intolerance of 50% in the control group and 75% in the intervention group the result is 79 evaluable subjects per group. We will aim to recruit 176 subjects total to allow for up to a 10% dropout rate.

8 General Analysis Considerations

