8.5.8 Practical Measures to Minimize Bias

The interim analysis is conducted by a PhD student in the Department of Statistics and Actuarial Science at Simon Fraser University, working under the direct supervision of the study statistician. Neither the statistician nor the student has a financial stake in the outcome of the trial. They receive only the data necessary to conduct the analysis and confirm its accuracy.

The results of the interim analysis are presented to the DSC by the study statistician and the DSC is charged with making a recommendation to the PI as to the advisability of continuing the trial.

OPT-JIA does not have a pharmaceutical sponsor and all medications tested in the trial are medications currently marketed in Canada and available as generic medications. The study PI, [name], serves as the trial sponsor in Health Canada submissions.

As per the OPT-JIA DSC Charter, [name] will consider the recommendation of the DSC. If the recommendation is to continue the trial to attain the newly calculated sample size, [name] will consider the feasibility of this approach given available study funding and the observed recruitment rate. No information will be made public until a final determination is made.

Because the intervention requires all parties in the trial to act differently from the control, there is no blinding in the trial, and hence no need for additional measures during the statistical analysis to preserve blinding.

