9.5 Treatment Compliance

Compliance with ondansetron and methotrexate is queried at each medical visit by the attending physician (local investigator) and reported in the physician case report forms. Parents are asked to confirm in writing in the parents' questionnaire how many ondansetron tablets were given to their child with the previous dose of methotrexate.

Since this is a pragmatic trial to test effectiveness in usual medical practice, there will be no pill counts or measurement of blood medication levels as part of this trial.

10 Efficacy Analyses

The final efficacy analysis will be conducted after the last recruited trial participant has had an opportunity to be followed for 60 weeks from the date of recruitment (52 weeks plus an 8-week window of observation and data entry). The final dataset will then be verified and locked.

As per the OPT-JIA protocol (V3, 2-Sept-2020), the final analysis will be an intention to treat analysis including all randomized participants irrespective of whether they completed the trial, received or not the trial interventions, or dropped out. A secondary modified per-protocol analysis will be conducted on those subjects who received the assigned intervention for at least 3 months or stopped medications before 3 months for intolerance or toxicity.

All statistical analysis will test the null hypothesis of no differences between intervention and control groups. The a priori alternative hypothesis is that the intervention group will have better outcomes than the control group.

Logistic regression models will be used to adjust effect estimates for post-randomization imbalances in the two groups (intervention, control). Baseline variables with a p value <0.1 in the baseline comparison of intervention and control groups will be considered post-randomization imbalances and adjusted for, if any.

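### The sample size is re-estimated for a final confidence interval above RR 1.2, but the final test only needs it above 1; 79 per group gives about 90% power for one rule and 39% for the other

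*SAP*

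**What the plan says.** - **Section 7 (Sample Size)** plans for 90% power at the 0.05 level, with expected success of 50% in control and 75% in intervention, working with the RR on the log scale: "the result is 79 evaluable subjects per group". Allowing for 10% dropout, the target is 176. No RR threshold is named.
- **Section 8.5.4 (Stopping Rules)** uses RR 1.2 as the boundary at the interim analysis, for futility and for superiority. The reason is clinical: "An increase in this proportion to <60% is deemed too small to justify the additional costs and risks of adding prophylactic ondansetron".
- **Section 8.5.7** re-estimates the sample size by simulation at the same 75% and 50%, looking for the number of further patients that will "maintain a 90% chance that the final analysis produces a 95% confidence interval for the relative risk that lies entirely above 1.2". It treats the proportion of simulated trials meeting that condition as the study's power.
- **Section 10 (Efficacy Analyses)** sets the null: "All statistical analysis will test the null hypothesis of no differences between intervention and control groups".
- **Section 10.1** gives the final decision rule for the primary endpoint: "the null hypothesis will be rejected if the confidence interval is entirely above 1".
- **Section 8.5.6** leaves alpha 0.05 − 0.0045 = 0.0455 for the final analysis.

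**The concern.** Sections 8.5.7 and 10.1 describe the same final analysis of the same relative risk, but attach different thresholds to it. One sets the trial's size and the other decides whether it succeeded. Section 15, which summarises the statistical changes, does not mention or explain the difference.

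Two things are at stake. First, section 8.5.8 makes the re-estimated number the basis of a practical decision: "If the recommendation is to continue the trial to attain the newly calculated sample size", the sponsor weighs its feasibility against funding and recruitment. Section 8.5.3 already worries that even the original target may be out of reach. A number computed for a stricter criterion than the final test uses could make a feasible trial look infeasible. Second, a final lower limit between 1 and 1.2 would succeed under section 10.1 but miss the target of section 8.5.7. That leaves room to argue, after the data are seen, about which one counts.

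**Working it through.** **Inputs.** Success 75% v 50% (sections 7 and 8.5.7), so RR = 1.5. Two-sided alpha 0.05 (sections 7 and 9), with 0.0455 left for the final analysis (section 8.5.6). Power 90% and 79 per group (section 7). Allocation 1:1 (section 6.3). Complete binary follow-up is assumed throughout.

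**Method.** Wald interval on the log RR. With n per group, SE² = [(1−0.75)/0.75 + (1−0.50)/0.50]/n = 1.3333/n. Success means that the lower limit exceeds the threshold R. Power was obtained by exact enumeration of both binomial arms, with the normal approximation as a check: power ≈ Φ[(ln 1.5 − ln R)/SE − 1.96].

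**Step 1: reproduce the plan's figure.** With R = 1, exact power is 89.8% at n = 78 and 90.3% at n = 79. The stated 79 is therefore the smallest n reaching 90% by this method. Allowing for dropout, 158/0.9 = 175.6, so 176. Formulas give similar sizes:
- log RR with pooled null variance: (1.96·√1.2 + 1.2816·√1.3333)²/0.4055² = 80.0;
- log RR unpooled: 1.3333·(1.96 + 1.2816)²/0.4055² = 85.2, so 86;
- standard two-proportion formula: 77.

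Whichever formula was used, the 79 fits a null RR of 1.

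**Step 2: the same 79 per group under the 8.5.7 target.** SE = √(1.3333/79) = 0.1299.

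| Rule | Normal approximation | Exact, alpha 0.05 | Exact, alpha 0.0455 |
|---|---|---|---|
| CI above 1 | Φ(0.4055/0.1299 − 1.96) = Φ(1.161) = 87.7% | 90.3% | 89.6% |
| CI above 1.2 | Φ(0.2231/0.1299 − 1.96) = Φ(−0.242) = 40.4% | 39.3% | 38.8% |

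**Step 3: size needed for 90% power, starting fresh.**

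| Rule | Exact, alpha 0.05 | Exact, alpha 0.0455 | Unpooled formula, alpha 0.05 |
|---|---|---|---|
| CI above 1 | 79 | 81 | 86 |
| CI above 1.2 | 267 | 273 | 1.3333·(1.96 + 1.2816)²/0.2231² = 281.4, so 282 |

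The exact ratio is 267/79 = 3.4. By formula it is (0.4055/0.2231)² = 3.3.

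**Step 4: illustration conditional on interim data.** Section 8.5.7 adds simulated patients to those already observed. Section 15 says "there were only 27 patients on whom success or failure had been definitively determined" but gives no results by arm. The 14/13 split and the success counts below are assumptions, and the 17 partially followed patients are left out. Further patients per group for 90% power at alpha 0.05:

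| Assumed successes (intervention, control) | CI above 1 | CI above 1.2 | Ratio of total N |
|---|---|---|---|
| 7/14, 8/13 | 97 | 315 | 3.0 |
| 9/14, 8/13 | 82 | 290 | 3.2 |
| 10/14, 7/13 | 66 | 262 | 3.5 |
| 11/14, 6/13 | 50 | 233 | 3.9 |
| 12/14, 5/13 | 28 | 201 | 5.2 |

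Total N is 27 plus twice the further patients per group; for the third row, (27 + 524)/(27 + 132) = 551/159 = 3.5.

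**The case against.** The best defence is that only section 10.1 states a final decision rule, and section 10 agrees with it. Section 8.5.7 sets a sizing target and nowhere says that success will be claimed only above 1.2. Sizing a trial so that it can probably exclude a clinically trivial effect, while testing a null of 1, is a legitimate choice, and section 8.5.4 gives a clinical reason for 1.2. An interval above 1.2 is also above 1, so the larger trial over-powers the section 10.1 test without invalidating it. Type I error is not affected. The interim data were extracted in October 2023, so the re-estimation may already have been done and acted on.

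Much of this is fair. A stricter bar for stopping early is not a defect, and 1.2 may be a deliberate target. But the SAP does not say so, and it presents the result as the study's power and as the continuation of an existing 90% chance. Neither is true of the final test in section 10.1 or of the original 79 per group. If 1.2 really is what the trial should show, section 10.1 lets a claim be made on less. Either reading requires a correction. That the real re-estimated number is unknown also stands, and it limits what can be said about harm already done.

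**Conclusion.** The inconsistency is real and should be resolved before the final analysis. At the planned 79 per group, power is about 90% for the section 10.1 rule and about 39% for the section 8.5.7 target (38.8% to 40.4% across the variants tried). The design therefore never had the 90% that section 8.5.7 says it will maintain. At the planning stage the two rules differ by a factor of about 3.4 in sample size. Under the assumed interim results the factor in total N runs from about 3.0 to 5.2.

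These figures rest on the plan's 75% and 50%, a Wald interval on the log RR and complete follow-up. The final analysis will use Kaplan-Meier estimates with censoring, which will change the exact values. The 79 itself is not in question. The SAP reports neither the re-estimated number nor the decision taken on it, so the consequence for the actual trial cannot be determined from the document.

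**What to change.** State one final success criterion and use it in sections 8.5.7 and 10.1. There are two ways:

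1. **If section 10.1 governs:** re-run the section 8.5.7 simulation with success defined as the lower limit of the final, alpha-adjusted, Kaplan-Meier-based interval exceeding 1. Report that number to the Data and Safety Committee and the sponsor. Keep 1.2 as the interim boundary and as a benchmark for interpreting the result.
2. **If 1.2 is the intended final rule:** write it into section 10.1 and into the null hypothesis in section 10. Restate the section 7 power as about 39% at 79 per group, with about 267 per group needed for 90% (273 at alpha 0.0455).

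In both cases remove the word *maintain* from section 8.5.7, or say which design and which criterion the 90% refers to. The cost is SAP wording and a re-run of an existing simulation; no new data or procedures are needed.
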